5.3 Modeling of clinical impact

In order to quantify the reduction of DPEs and OCEs in clinically relevant terms and to resolve ambiguities associated with purely dosimetric outcome indices, radiobiological isoeffect models and outcome prediction models will be used. To account for local delivery variations (dose rate, fraction size, linear energy transfer) in relation to local radiosensitivity, we will use the isoeffective quantity, biologically effective dose or BED, derived from the linear-quadratic (LQ) model. LQ parameters from photon therapy clinical data will be adapted to account for the fact that linear energy transfer varies along the proton path, producing variations in relative biological effectiveness (RBE) which is maximized near each pristine Bragg peak. As higher linear energy transfer (LET) produces more single-and double-strand breaks, tissues near the distal SOBP act more like early responding tissues with higher α/β compared to photon treatments. Assuming a first-order approximation for the dependence of the proton α/β parameter on LET (evaluated by TOPAS), it can be approximated by $\alpha/\beta = \alpha/\beta + \chi \alpha/\beta \cdot \text{LET}$, where α/β and χ are photon therapy LQ parameters. We found χ to be $0.0079 \text{ } \mu\text{m keV-1 Gy-2}$ from fitting the experiment data²⁰ to proton therapy. BED, rather than physical absorbed dose, will be used as a dose accumulation parameter, giving rise to BED volume-histograms.

Outcome models take this process one step further by transforming a complex 3D dose distribution into a single number that is a surrogate for a clinically measurable endpoint. Equivalent uniform dose (EUD) was introduced by Niemierko in 1997 as the primary surrogate for tumor control probability (TCP). For quantifying normal tissue responses, we use Mohan's approach, which reduces the cumulative BED volume histogram to a single equivalent dose using generalized EUD (gEUD) and applies the LKB model to compute the normal tissue complication probability (NTCP).

We will quantify difference in tumor control and normal tissue complications between VCT trial arms A and B for each relevant tumor and normal-tissue endpoints. For brain, the complication endpoints to be reviewed include brainstem injury, panophthalmitis/blindness and brain necrosis; for lung, the complication endpoints to be reviewed include esophagitis, pneumonitis, and cardiac morbidity.

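### The LET correction in Section 5.3 does not balance in units, and with no BED formula stated the plan leaves the sign of the LET effect open

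*Combined protocol and SAP*

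**What the plan says.** Section 5.3 (Modeling of clinical impact) explains that LET varies along the proton path, "producing variations in relative biological effectiveness (RBE) which is maximized near each pristine Bragg peak". It infers that "tissues near the distal SOBP act more like early responding tissues with higher α/β compared to photon treatments". It then gives the rule: "Assuming a first-order approximation for the dependence of the proton α/β parameter on LET (evaluated by TOPAS"), proton α/β is taken as the photon α/β plus χ times α/β times LET. The printed formula carries the same symbol on both sides, so subscripts have probably been lost.

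The value given is χ = 0.0079 µm keV⁻¹ Gy⁻². The section makes two statements about its origin. α/β and χ "are photon therapy LQ parameters", and χ was found by fitting experimental data to proton therapy.

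BED from the LQ model replaces physical dose as the quantity accumulated. The BED volume histogram is reduced to gEUD and passed to the LKB model for NTCP. EUD is named as the surrogate for TCP, without saying whether it is computed from BED or from physical dose. The section does not give a BED equation, a reference radiation, a treatment of β, or values for the LQ parameters other than χ.

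**The concern.** There are two separate problems. First, a term in one unit is added to a quantity in another, so the rule cannot be coded as written without someone deciding what it was meant to say. Second, the only LET adjustment stated is a rise in α/β. In the ordinary LQ expression a higher α/β lowers BED at fixed dose. Followed literally with that expression, the plan would assign less biological effect where it says effectiveness is greatest.

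At stake is exploratory objective 2.2(c), simulated patient outcomes. Section 1.2 says dose prediction errors arise mainly at the distal edge of the beam, and Section 5.3 places the LET-related change in tissue response near the distal SOBP. An LET correction with the wrong sign would therefore act where the SECT and DECT plans are expected to differ.

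**Working it through.** **Inputs.** From Section 5.3: the form of the rule and χ = 0.0079 µm keV⁻¹ Gy⁻². Assumed, because the documents do not give them: dose per fraction d = 2 Gy, photon α/β = 3 Gy (2 and 10 Gy where stated), LET values in keV/µm, and photon α where it is needed. The value of χ cannot be reproduced, because the fitted data are not in the documents.

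**1. Units.** α is in Gy⁻¹, β in Gy⁻², α/β in Gy and LET in keV µm⁻¹.
- As printed: χ·(α/β)·LET = (µm keV⁻¹ Gy⁻²)(Gy)(keV µm⁻¹) = Gy⁻¹, the units of α.
- If the second α/β is only a label on χ: χ·LET = Gy⁻², the units of β.
- Neither can be added to α/β, in Gy. To balance, χ would have to be in µm keV⁻¹ in the first case, or Gy µm keV⁻¹ in the second.

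**2. Numbers at face value, ordinary BED.** Take (α/β)_p = (α/β)(1 + 0.0079·LET) and BED/D = 1 + d/(α/β)_p. With α/β = 3 and d = 2 the value without the LET term is 1 + 2/3 = 1.6667.

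| LET (keV/µm) | (α/β)_p (Gy) | BED/D | Change |
|---|---|---|---|
| 2 | 3.047 | 1.6563 | −0.6% |
| 10 | 3.237 | 1.6179 | −2.9% |
| 15 | 3.356 | 1.5960 | −4.2% |

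At LET 10 the fall is 3.7% for α/β = 2 and 1.2% for α/β = 10.

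**3. Same proportional rise, photon-referenced BED.** Assign the factor 1 + 0.0079·LET to α, hold β fixed, and write BED/D = α_p/α_photon + d/(α/β)_photon. At LET 10 and α/β = 3: 1.079 + 0.6667 = 1.7457, and 1.7457/1.6667 gives +4.7%. Over α/β = 2 to 10 the range is +4.0% to +6.6%. The sign has reversed, and only the BED formula is different.

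**4. Term placed on α, as its printed units suggest.** α_p = α_photon + χ·(α/β)·LET. At LET 10 and α/β = 3 the increment is 0.0079 × 3 × 10 = 0.237 Gy⁻¹. Photon-referenced BED/D is then:
- assumed α_photon = 0.5 Gy⁻¹: 1 + 0.237/0.5 + 0.6667 = 2.1407, or +28%;
- assumed α_photon = 0.2 Gy⁻¹: 1 + 0.237/0.2 + 0.6667 = 2.8517, or +71%.

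**5. Moving the term to α is not enough by itself.** If BED/D is written 1 + d/(α_p/β), it still falls. At α/β = 3 and LET 2.5, with α_photon = 0.3 Gy⁻¹ (so β = 0.1 Gy⁻²), α_p/β = (0.3 + 0.05925)/0.1 = 3.5925 and BED/D = 1.5567, or −7%. With α_photon = 0.1 Gy⁻¹ the change is −15%. The reference radiation has to be stated as well.

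**The case against.** The strongest reply is that the plan contains no BED equation, so a fall in BED is a consequence of a formula supplied by the reader. Section 5.3 speaks of adapting LQ parameters, in the plural, which leaves room for an α_proton/α_photon term, and step 3 shows that with such a term BED rises. The statement about higher α/β is also not wrong in itself: raising α at fixed β raises α/β. This stands. The sign is conditional on the BED formula, and the point is worded that way.

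It can also be said that the formula has visibly lost notation, so the mismatch may be a misprint. Lost subscripts alone do not remove it: both readings in step 1 fail, and the prose also directs the correction at the proton α/β. A misprinted unit for χ remains possible, and the documents cannot exclude it. For the same reason it would be too strong to say that χ can only belong to α.

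A reader might infer that every TCP and NTCP result is biased. The documents do not support this. The implementation is unknown, and no TCP, NTCP or between-arm difference has been calculated here. TCP is not explicitly tied to BED, and the outcomes are A-versus-B differences under one shared model. A shared model does not guarantee that the error cancels, since the arms differ in where dose falls and NTCP is nonlinear, but the net effect has not been estimated. Nor do the +28% and +71% in step 4 measure an error in the plan. They come from a replacement equation with assumed photon α.

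**Conclusion.** The point holds in a limited form. The LET rule and the units of χ are inconsistent under both readings checked. With no BED equation given, the plan does not determine even the direction of the LET effect. Under the ordinary LQ form with only α/β raised, BED moves opposite to the stated RBE, by about 0.6% to 4% over LET 2 to 15 keV/µm at the assumed α/β of 3 Gy and 2 Gy per fraction.

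The reach is the BED volume histograms and the gEUD/LKB NTCP results under exploratory objective 2.2(c). The size of any bias in the A-versus-B contrast is not known. DPE and OCE are defined on dose-volume indices (Section 5.2.3), and the sample size rests on DVH surrogates and plan differences (Section 7.0), so none of these depends on the equation. It should be corrected before the outcome modeling is run.

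**What to change.** - Check the equation and χ against the fit from which they came, and restate both with subscripts and consistent units.
- If χ was fitted to α, as its units suggest, write α(LET) = α_photon + χ·(α/β)_photon·LET with β held at its photon value. If it was fitted to α/β, correct the units of χ and refit if needed.
- In either case define BED against the photon reference, with β fixed: the sum over fractions of d·[α(LET)/α_photon + d/(α/β)_photon].
- Before use, verify that BED rises with LET at fixed physical dose.
- State whether the EUD used for TCP is computed from BED or from physical dose.
- Reconcile the description of χ as a photon LQ parameter with the statement that it was fitted to proton therapy.

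The cost is a corrected equation in Section 5.3, a small code change and possibly a refit of χ. Nothing changes for patients or for data collection.

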6.0 SAFETY MONITORING AND REPORTING

6.1 Potential Risk

In addition to potential loss of privacy, the delivery of small additional doses of ionizing radiation associated with the additional DECT research scans poses a small risk of carcinogenesis to patient subjects. The total additional radiation dose for the dual-energy data acquisition will be less than 6 cGy per imaging session, or a total of no more than 24 cGy over the entire treatment course. The potential risk of cancer death due to this modest additional dose of ionizing radiation is theoretical and acknowledged to be uncertain. It is estimated that there is a 0.0002 incidence of increased cancers, over a risk period of 30 years, per 1 cGy radiation. No contrast media or other invasive procedures will be required.

6.2 Protection against Risk

The potential risk of increased radiation exposure due to increased imaging is currently only known from theoretical analyses. It is estimated that there is a 0.0002 incidence of increased cancers, over a risk period of 30 years, per 1 cGy radiation. This small radiation dose will be overwhelmed by therapeutic doses (30-90 Gy) administered to the region being imaged. There are no study-related limitations on patient care. No subjects will be enrolled prior to IRB approval. The imaging systems to be used are all FDA approved devices. The risk to patient privacy will be mitigated by anonymizing the images and raw datasets, so that patient identity is known only to the protocol PI and data managers, prior to processing the data.

6.3 Potential Benefits of the Proposed Research to the Subjects and Others

The protocols of this project will not alter the participating subject's therapy beyond the limits specified in the eligibility requirements and protocol conduct. In particular, these protocols place no limits on the use of the acquired imaging data to manage the patient's radiation therapy. The treating radiation oncologists may use this imaging data and its results to improve the participating subject's therapy, provided that all applicable FDA and IRB guidelines are followed. Beyond this possibility, no direct benefit to the patient is expected. The alternative is not to participate in the study.

The overall hypothesis of this study is that dual-energy CT imaging, when coupled with appropriate image reconstruction and analysis techniques, can be used to accurately map the radiological properties (total, scattering, and photoelectric cross sections; stopping power ratios and multiple-scattering cross sections) of human tissue on a voxel-by-voxel basis. Moreover the data will provide preliminary data to design a broader trial to assess the hypothesis that cross-section imaging significantly improves dose delivery accuracy. This will increase the accuracy with which cancers can be treated with charged particle radiation therapy and reduce the incidence of normal tissue toxicity. The additional normal-tissue dose sparing may improve outcomes to future patients undergoing treatment by reducing normal tissue complications or enabling tumor dose escalation.

6.4 Adverse Events

There are no anticipated study-related adverse events, aside from those listed in the Potential Risks section (above). All unanticipated adverse events will be reported to the IRB, as required within 10 days of notification. All serious unanticipated adverse events will be reported within 24 hours.

The descriptions and grading scales found in the revised NCI Common Terminology Criteria for Adverse Events (CTCAE) version 4.0 will be utilized for adverse event reporting.

6.5 Data and Safety Monitoring Plan

The study principal investigator and study coordinator will monitor for breaches of confidentiality and other adverse events on an ongoing basis. Once the PI or study coordinator becomes aware of a reportable adverse event, the event will be reported to HRPO and QASMC according to institutional guidelines. This study does not require QASMC audit or submission of DSM reports.

7.0 STATISTICAL CONSIDERATIONS

Based on the differences and patient-to-patient variability from our preliminary data, recruiting 20-25 patients for each site (depending on DVH endpoint) is sufficient to detect 2%-3% changes in absolute DVH surrogates, e.g., 2% changes in heart V30 for 20 NSCLC patients, with 80% power at 95% level of confidence from reducing range uncertainty from 3.5% to 1.0%. Because each patient subject is their own control, we assumed a moderate positive correlation between treatment arms of 0.5, consistent with that observed in other image-guided radiation therapy VCTs40. For lung cancer, we hypothesize that we will observe >40% reductions in esophageal V60 (corresponding to reduction of $\geq g2$ esophagitis from 60% to 39% (71), a reduction >30% in mean heart dose (from 8 Gy to 5 Gy, reducing relative risk factor for late cardiac disease from 1.60 to 1.3727, and total lung V20 from 15% to 10% (lowering risk of radiation pneumonitis from 15% to 8%48). Likewise, greater precision towards predicting radiation dose to neighboring neural structures such as the optic chiasm, optic nerve, brainstem, and eye is clearly important. Tumor volumes frequently abut these structures, creating situations where the physician chooses to underdose the tumor target, rather than risk severe toxicity in normal tissue resulting in complications such as blindness.

The hypothesis to be tested is that Monte Carlo treatment plans based upon standard of practice single-energy CT cross-section mapping differ significantly from Monte Carlo plans using cross-section maps derived from our proposed quantitative dual-energy CT (DECT) imaging methodology. Neither the expected magnitude of the difference nor its variability is known. However, from the literature and our preliminary studies, a minimum of 10%-15% difference might be considered clinically significant and the standard deviation of the difference is expected to be about 15%. Using a paired t-test, a sample size n=20 per group would enable us to detect differences of 15% and 12% for percent standard deviations of 15% and 10%, respectively, with 80% power at the 5% significance level. If we relax the significance requirement to 10% (appropriate for a preliminary/exploratory study), differences of 13% and 8.5% will be detectable under these conditions.

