1.0 BACKGROUND AND RATIONALE

1.1 Proton Beam Therapy

Proton beam therapy (PT) is a rapidly evolving modality with high potential for improving radiation therapy clinical outcomes because of its ability to deliver high doses to the target tissue while sparing surrounding normal tissues. Because of the finite range of protons in tissue, proton dose rapidly peaks at a maximum value (call the “Bragg Peak”) near the end of the charged particle range and then abruptly falls to negligible levels. By properly modulating the proton energy, and superposing many Bragg Peaks (the “spread-out Bragg peak” or SOBP), a single-field dose distribution is created which uniformly treats the tumor and falls to negligible levels within a few mm beyond the distal tumor margin, thereby sparing almost completely normal tissues located distal to the tumor. However, PT dose delivery is very sensitive to the physical characteristics of the tissues in the beam’s path. Both the magnitude and position of the Bragg peak depends on the composition and density tissue of tissues traversed by the protons. Recommended {ICRU, 1989 #1028; ICRP, 2003 #904} organ/tissue compositions and densities, available for radiotherapy planning, are based upon historic (mostly from 1930-1960) tissue sample measurements {White, 1988 #1030; Woodard, 1986 #1031; Hammerstein, 1979 #1032} with large variations within the suggested values {Brooksby, 2006 #1052; Dance, 1999 #1033; Geise, 1996 #993}. These are potentially imprecise values that may vary significantly from patient-to -patient and within a single patient. Due to the aforementioned uncertainties in tissue composition and density, it is customary to add a 3.5% (about 4 mm for 12 cm range protons) to ensure adequate tumor coverage in the face of these so-called proton range uncertainties. Unfortunately, these safety margins significantly reduce the potential for sparing normal tissue.

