Uncertainty in proton range is incorporated into proton plan optimization in two ways: safety margin and robust optimization. Safety margin involves expanding CTV and OAR contours (generally by 3.5% of proton range) as recommended by ICRU 50 and 62. Recent studies have demonstrated that robust optimization in proton therapy produces more consistent and predictable dose distribution through the whole treatment course. Given the PDFs describing various uncertainties (setup, organ motion, and true vs. apparent SPR values), robust optimization selects multiple worst case scenarios (instances of patient anatomy and SPR assignments) from the ensemble of all possible instances described by the PDFs. The optimizer then optimizes the plan to satisfy the planning constraints and goals simultaneously on the multiple worst-case scenarios. The resultant plan is robust in the sense that acceptable outcomes will be realized even in the face of the most unfavorable random outcomes (positioning and SPR errors) that are likely to occur. In clinical practice, volumetric imaging greatly reduces the uncertainty associated with setup and sheds light on pre-treatment reoptimization of the treatment plan. As the range uncertainty becomes the largest uncertainty in plan optimization, accurate information on proton stopping power helps the optimizer achieve a more optimal plan.

Patient participation will be limited to having a DECT instead of the standard SECT. That single DECT session will be used to generate two treatment plans; one using standard range uncertainty margins and the second using exact measures of tissue density from the DECT to generate a mock treatment plan for comparison. We expect that the mock treatment plan will have tighter margins around the tumor and spare more normal tissue. Eligible patients

will either have lung cancer or cancer of the brain or base of skull. We have chosen these two patient populations because the tumor is adjacent to air densities where range uncertainty is greater, the problem poses the greatest technical challenge, and reducing the projected toxicity to critical structures would be clinically most meaningful (i.e. reducing dose to the esophagus or optic nerve).

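### For the dose prediction error (Arm A versus B1), the only stated test looks at the mean signed difference, so errors in both directions could cancel and go unreported

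*Combined protocol and SAP*

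**What the plan says.** Section 7.0 of the combined protocol and SAP gives the hypothesis without a direction or a named dose metric: "The hypothesis to be tested is that Monte Carlo treatment plans based upon standard of practice single-energy CT cross-section mapping differ significantly" from plans based on the DECT method. One test is named, in the sizing statement: "Using a paired t-test, a sample size n=20 per group would enable us to detect differences of 15% and 12" percent, for SDs of 15% and 10%, at 80% power and the 5% level. On the size of difference that matters and its spread, the section says that "a minimum of 10%-15% difference might be considered clinically significant and the standard deviation of the difference is expected to be about 15" percent.

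Section 5.2.2 says that the virtual trial will quantify dose prediction errors (DPE) and optimization-convergence errors (OCE). Section 5.2.3 defines DPE as the B1 index minus the A index, divided by the B1 index, with its sign kept. OCE compares B2 with B3.

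Other sections are concerned with error that varies between patients. Section 1.1 says of the recommended tissue compositions and densities: "These are potentially imprecise values that may vary significantly from patient-to -patient and within a single patient". Section 1.2 introduces robust optimization with "Given the PDFs describing various uncertainties (setup, organ motion, and true vs. apparent SPR values" and the other sources of error. The primary objective (2.1) is about patient-specific distributions. Section 7.0 also describes "greater precision towards predicting radiation dose to neighboring neural structures" as important. Nowhere do the documents plan an estimate of spread, an absolute error, limits of agreement, or a share of patients beyond a given error.

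**The concern.** A paired t-test asks whether the mean signed difference is zero. For DPE, a patient whose dose was over-predicted offsets one whose dose was under-predicted, and the spread between them enters only as the noise term. If SECT errors run both ways across patients, the mean can be small while many patients have sizeable errors, and the result is then likely to be non-significant.

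The trial would have collected the data needed to describe those errors but would have no stated analysis that does so. Section 6.3 says that the data will help to design a broader trial, so a result taken as little SECT-DECT difference could carry forward.

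**Working it through.** **Inputs.** From Section 7.0: paired t-test, n = 20, 5% level, SD of the difference 15% (alternative 10%), difference of interest 10%-15%. From Section 5.2.3: DPE is signed. Assumed: normal differences, and a two-sided test, because sidedness is not stated and the hypothesis has no direction. The mean difference is not given, so a range is shown.

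**The plan's own figure.** Power is the probability that a noncentral t with 19 degrees of freedom and noncentrality (mean/SD) × √20 falls beyond ±2.093. Solving for 80% power gives detectable mean differences of 9.9% (SD 15%) and 6.6% (SD 10%). The stated 15% and 12% are not reproduced; at those values power is 98.9% and 99.9%. That is a separate matter. The figures below use only the SD, n and level.

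**Rejection rate against individual errors, SD 15%, n = 20.** The share of patients beyond ±10% is [1 − Φ((10 − mean)/15)] + Φ((−10 − mean)/15).

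| Mean difference | Noncentrality | Chance of rejecting | Patients beyond ±10% |
|---|---|---|---|
| 0 | 0 | 5% | 2 × [1 − Φ(0.667)] = 50% |
| 5% | 5/15 × 4.472 = 1.491 | 29% | 0.369 + 0.159 = 53% |
| 10% | 10/15 × 4.472 = 2.981 | 81% | 0.500 + 0.091 = 59% |

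At mean 0, the share beyond ±15% is 2 × [1 − Φ(1)] = 32%, the mean absolute difference is 15 × √(2/π) = 12%, and the 95% limits of agreement are ±1.96 × 15 = ±29%. In 200,000 simulated trials at mean 0 the rejection rate was 5.1%. With SD 10% and mean 0, 32% of patients exceed 10%, 13% exceed 15%, and the test again rejects about 5% of the time.

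At a mean of exactly zero, adding patients leaves the rejection rate at 5%. At any other mean, adding patients raises it.

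**What n = 20 can say about spread.**
- SD of 15%, 95% CI: 15 × √(19/32.85) to 15 × √(19/8.91), or 11.4% to 21.9%.
- Standard error of each limit of agreement: 15 × √(1/20 + 1.96²/(2 × 19)) = 5.8 percentage points.
- 10 of 20 patients beyond a cutoff: exact 95% CI about 27% to 73%.

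**The case against.** The strongest reply is that the plan's quantified hopes all have a direction: tighter margins and more sparing (Section 1.2), and lower esophageal V60, mean heart dose and lung V20 (Section 7.0). A mean test suits those, and it suits B2 versus B3. This stands, and the point does not extend to them. Section 7.0 also does not tie its hypothesis to A versus B1; it could equally mean the combined contrast of Section 5.2.3. That too is fair, but then DPE has no stated inference at all.

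No section says that signed dose differences centre on zero. The remarks in Sections 1.1 and 1.2 concern tissue values and scenario selection, and dose-volume indices near a steep distal edge need not respond equally to overshoot and undershoot. Cancellation is therefore a possibility and not a forecast, and a mean shift of 10% would be found with 81% power. Against this, Section 7.0 says that neither the magnitude nor the variability of the difference is known, so a large mean shift cannot be relied on.

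A reader might infer three stronger things, none of which the documents support:
- **That the 15% is the range uncertainty under study.** It is the SD of a plan difference whose metric is unnamed. Range uncertainty is a separate figure, 3.5% to be reduced to 1.0%.
- **That a larger spread means worse SECT.** The spread also carries anatomy, the sensitivity of the dose index, and error in the DECT map, since B1 is itself an estimate of delivered dose.
- **That the plan sets 10%-15% as a per-patient cutoff.** It is given as a difference worth detecting.

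Finally, nothing says that a non-significant result will be taken as agreement, and the dosimetric aims are exploratory. That lowers the stakes but leaves the gap.

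**Conclusion.** The point holds for A versus B1. The only stated test targets the mean of a signed error, and no planned summary would show large errors that differ in sign between patients. If differences are normal with SD 15% and n = 20, a mean of 0 to 5% leaves 50% to 53% of patients beyond 10%, with a 5% to 29% chance of a significant result. These figures rest on normality, on the plan's SD, on a small mean that the documents neither state nor exclude, and on using 10% as a reference value for individual patients. The paired t-test is not wrong in itself; it is incomplete for this contrast. Adding the missing summaries is a cheap improvement to an exploratory analysis.

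**What to change.** In Section 7.0, for A versus B1 only:

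1. Keep the paired t-test, described as the test for systematic error.
2. Add the SD or limits of agreement of the signed difference, and the mean or median absolute difference, each with a 95% CI.
3. Add the proportions of patients with an absolute difference of at least 10% and at least 15%, with exact 95% CIs. Describe the two values as reference points taken from the plan's 10%-15%.
4. Where the B1 index is small and the fractional DPE becomes unstable, also report the difference in absolute DVH units.
5. State that a non-significant t-test alone will not be read as agreement between SECT and DECT.

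The cost is wording and a few summaries of the same 20-25 pairs per site; no scans or patients are added. The downside is the wide intervals at n = 20 shown above. The interval for the SD also leans on normality, which is a further reason to report an absolute-error summary beside it.

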2.2 Exploratory Objectives

To assess the impact of DECT tissue property mapping on

- a.) plan quality
- b.) dose-delivery accuracy, and
- c.) simulated patient outcomes

for locally advanced lung, H&N and brain tumor patients treated with proton therapy.

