5.2.2 Dose Evaluation Schema

We will perform a VCT for each tumor site to assess quantitatively dose prediction errors (DPEs) and optimization-convergence errors (OCEs) associated with more approximate SECT stopping power mapping. In the VCT, every patient will go through the current clinical workflow for planning and dose delivery, where SECT is the primary image for treatment planning and conventional range uncertainty of 3.5% is employed. The SECT data uses one of the two DECT data sets. The DECT images will be used differently in Arm A and Arm B of the VCT.

In Arm A, patients are treated with treatment plans optimized and calculated on the SECT data. Plan dose is re-calculated for every patient with the clinical plan in a Monte Carlo dose calculation engine for better accuracy. We will use TOPAS, an extension of Geant4 simulation toolkit, as the dose calculation engine.

In Arm B, the DECT data is used for plan optimization and dose calculation. In Arm B1, DECT data is used to estimate the actual dose delivered using the clinical plan based on SECT data. In Arm B2, the plan is re-optimized on DECT data with the conventional uncertainty margin of 3.5% of proton range. In Arm B3, the plan is re-optimized on DECT data with the SPR uncertainties derived from the patient-specific uncertainty model developed.

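### The four detectable differences given for the paired t-test with n=20 do not follow from 20 pairs, and two of them contradict each other; the error is conservative

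*Combined protocol and SAP*

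**What the plan says.** All the figures are in the second paragraph of Section 7.0. It takes "a minimum of 10%-15% difference might be considered clinically significant and the standard deviation of the difference is expected to be about 15" percent as its planning values. It then says, for a paired t-test with 80% power at 5% significance, "a sample size n=20 per group would enable us to detect differences of 15% and 12% for percent standard deviations of 15% and 10" percent. If significance is relaxed to 10%, "differences of 13% and 8.5% will be detectable under these conditions". Sidedness is not stated.

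The first paragraph of Section 7.0 plans on "recruiting 20-25 patients for each site (depending on DVH endpoint"). Because patients serve as their own controls, it adds that "we assumed a moderate positive correlation between treatment arms of 0.5". Section 5.2.2 confirms that the analysis is done site by site: "We will perform a VCT for each tumor site". The comparison belongs to Section 2.2, Exploratory Objectives, which begins "To assess the impact of DECT tissue property mapping on".

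**The concern.** For a paired t-test, the detectable difference is fixed by the number of pairs, the significance level, the power and the SD of the paired difference. Section 7.0 gives all of these except sidedness, so its figures can be checked directly. Two things looked wrong. A difference of one full SD (15% at SD 15%) is far more than 20 pairs need for 80% power. And two differences in the ratio 15 to 12 cannot come from SDs in the ratio 15 to 10.

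These are the only power figures in the plan with a stated SD; the claim of detecting 2%–3% changes in DVH surrogates gives none and cannot be checked. As printed, 20 patients at the expected SD have 80% power only at the top of the 10%–15% range at the 5% level, and only at 13% at the 10% level. A reader judging the study's sensitivity, or deciding whether the relaxed level is needed, would be working from wrong numbers.

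**Working it through.** **Inputs, all from Section 7.0.** Paired t-test; n = 20; power 80%; alpha 0.05 or 0.10; SD of the difference 15% or 10%. Assumptions: n = 20 means 20 pairs per tumor site; two-sided test, with one-sided tried as well.

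**Formula.** With n pairs, df = n − 1 and the noncentrality parameter is (Δ/SD)·√n. Two-sided power is the probability that a noncentral t with these parameters falls outside ±t(1 − α/2, df). Set this to 0.80 and solve for d = Δ/SD; the detectable difference is then d × SD.

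**Attempt to reproduce the plan's figures.** For 20 pairs, two-sided, d = 0.660 at alpha 0.05 and 0.577 at alpha 0.10. One-sided, d = 0.577 and 0.485. For two independent groups of 20, df = 38 and the noncentrality parameter is (Δ/SD)·√(n/2). The other readings follow in the same way:

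| Reading | SD 15, 5% | SD 10, 5% | SD 15, 10% | SD 10, 10% |
|---|---|---|---|---|
| Stated in the plan | 15 | 12 | 13 | 8.5 |
| 20 pairs, two-sided | 9.91 | 6.60 | 8.65 | 5.77 |
| 20 pairs, one-sided | 8.65 | 5.77 | 7.28 | 4.85 |
| Two-sample, 20 per group, two-sided | 13.64 | 9.09 | 12.01 | 8.01 |
| SDs per arm, correlation 0, 20 pairs, two-sided | 14.01 | 9.34 | 12.24 | 8.16 |
| 20 pairs, two-sided, 99% power | 15.18 | 10.12 | 13.83 | 9.22 |
| 10 pairs, two-sided | 14.94 | 9.96 | 12.79 | 8.53 |

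If the SDs were per arm with the plan's correlation of 0.5, the SD of the difference would be SD × √(2(1 − 0.5)) = SD, which returns the second row. No reading with n = 20 gives the stated set. Ten pairs match three of the four values after rounding, but the documents do not show where the figures came from, so this is only an observation.

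**Size of the discrepancy against 20 pairs, two-sided.**

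| Stated difference | SD | Alpha | Correct difference | Overstatement | Power at stated difference | Pairs needed for 80% |
|---|---|---|---|---|---|---|
| 15 | 15 | 0.05 | 9.91 | 15/9.91 = 1.51 | 98.9% | 10 |
| 12 | 10 | 0.05 | 6.60 | 12/6.60 = 1.82 | 99.9% | 8 |
| 13 | 15 | 0.10 | 8.65 | 13/8.65 = 1.50 | 98.2% | 10 |
| 8.5 | 10 | 0.10 | 5.77 | 8.5/5.77 = 1.47 | 97.8% | 11 |

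**Internal consistency.** At fixed n, alpha and power, d is a constant, so the two differences must stand in the ratio of the SDs, 15/10 = 1.5. At the 10% level, 13/8.5 = 1.53, which agrees within rounding. At the 5% level, 15/12 = 1.25, which does not. With 8 pairs, for example, the values are 17.34 and 11.56: a figure near 12 at SD 10 goes with about 17, not 15, at SD 15.

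**What 20 pairs can do at the lower end of the range.** For Δ = 10% and SD = 15%, d = 0.667. Two-sided power is 80.7% with 20 pairs and 78.5% with 19 at the 5% level, and 89.0% and 87.5% at the 10% level.

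**The case against.** The arithmetic is not open to serious dispute, but its importance is. The error understates what the design can do, no patient numbers change, and the comparison is exploratory. The plan itself says that neither the size of the difference nor its variability is known, so these are rough planning values. Recruitment of 20–25 per site also has a separate justification in the first paragraph of Section 7.0. All of that stands, and it limits the weight of the point.

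A second objection is that a difference with 80% power is not a detection floor, and that completed results are read from the estimate and its confidence interval. At SD 15% and n = 20, an observed difference above 2.093 × 15/√20 = 7.0% is significant at the two-sided 5% level whatever Section 7.0 says. This is fair. The harm lies in a wrong account of the design's sensitivity, which could colour how a null result is discussed; the test itself is unaffected.

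Third, the words about n per group may mean patients per tumor-site group, which is compatible with a paired test. That is a reasonable reading and the one used here, so the phrase is an ambiguity to clear up rather than an error.

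None of these objections makes the four figures follow from their stated inputs, or lets 15% and 12% hold together.

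**Conclusion.** The concern holds. With 20 pairs and 80% power, the two-sided detectable differences are 9.9% and 6.6% at the 5% level and 8.7% and 5.8% at the 10% level, for SDs of 15% and 10%. The plan's figures exceed these by 47% to 82%. The 15% and 12% are incompatible at any sample size.

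The result rests on n = 20 meaning 20 evaluable pairs per site, on the SDs being those of the paired difference, as the plan says of its expected 15%, and on a two-sided test. One-sided testing enlarges the discrepancy. The label conservative depends on 20 pairs actually being analysed: with only 10, the stated 15%, 13% and 8.5% would be about right and there would be no reserve.

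This should be corrected, but it does not threaten the study. The useful consequence is that 20 evaluable pairs reach a 10% difference at SD 15% without relaxing the 5% level, though with almost nothing to spare.

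**What to change.** Replace the two sentences in Section 7.0 with wording such as:

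*With 20 evaluable patients (pairs) per site, a paired t-test has 80% power at the two-sided 5% level to detect differences of 9.9% and 6.6% for standard deviations of the difference of 15% and 10%, respectively; at the two-sided 10% level the corresponding differences are 8.7% and 5.8%.*

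The sponsor should confirm sidedness; if the test is one-sided, the figures are 8.7% and 5.8% (5%) and 7.3% and 4.9% (10%). If 25 per site is the upper target, add the two-sided values for 25 pairs: 8.8% and 5.8% (5%) and 7.7% and 5.1% (10%). It would also help to say that power for a 10% difference at SD 15% falls to 78.5% at the two-sided 5% level if only 19 pairs are evaluable. Whether to keep the 10% level as an exploratory option is the sponsor's choice; only its figures need correcting.

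The cost is a wording change in Section 7.0, with no effect on patient numbers or procedures.
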